6.1.3 Fetal MRI

We routinely perform late-gestational MRI for fetal TGA before birth to examine fetal hemodynamics and the brain. Fetal MRI poses no known risks to the mother and her fetus. Baseline and MH MRI will be performed as usual with a clinical 1.5T MR system in the CDIU. No sedation or invasive techniques will be required to perform MRIs on pregnant women. The MRI study will take a maximum of 90 minutes including MH study, which is expected to take maximally 45 minutes. The subjects will be fitted with their usual supply of oxygen via a face mask during MRI. The same amount of O₂ at the same flow rate will be administered as described above.

As with all our fetal MRI studies, a standard multichannel body surface coil will be placed over the maternal abdomen and imaging performed for a maximum of one hour. MR flow assessments will be acquired according to our previously published technique to examine the distribution of blood flow across the fetal circulation (15). The PC MR acquisitions will be analyzed using a commercial software (Q-flow, Medis) and the oximetry measurements will be analyzed using a region of interest placed over the central 50% of the vessel diameter on the T2 map, according to our previously published techniques (15,16). The imaging protocol has been detailed in previous publications and includes T1 and T2 weighted imaging, diffusion tensor imaging, MR spectroscopy and brain volumetry (15,17). MR oximetry will be recorded in the ascending aorta (AAo), superior vena cava (SVC), descending thoracic aorta (DAo), umbilical vein (UV) and main pulmonary artery (PA). Oxygen content at baseline and during MH will be measured offline at the level of the LV/MPA, RV/AAo and DAo. Blood flow quantifications (baseline and MH; cine-phase contrast) will be made in the AAo, DAo, main and branch PAs, SVC, IVC, UV and DA. Other variables will include estimated hematocrit (HCT), fluximetry, brain volumetry (baseline; 3D steady state), cDO₂ and cVO₂ (baseline and MH; T2 mapping) to measure oxygen consumption. Oxygen supplementation will be stopped once the above imaging variables have been obtained or after a maximum of 45 minutes (5 minutes initiation + 40 minutes MRI) if the test cannot be completed within this time frame. No further research related measurements will be obtained once the MH has terminated.

The MRI data will be used to calculate right ventricle cardiac output, left ventricle cardiac output, combined ventricle output, pulmonary artery flow, aorta-pulmonary collateral flow, foramen ovale flow and aortic isthmic flow.

6.1.4 Neonatal Data

Newborns with antenatally diagnosed TGA are routinely transferred to the Critical Care Unit immediately after their delivery for the preoperative management. Unless a VSD is large enough to allow discharge home with adequate oxygen saturations and to delay surgery to later in infancy, a neonatal ASO is the treatment of choice and mainly completed during the first week of life. Early neonatal preoperative procedures may include BAS and/or the use of IV prostaglandin to improve the oxygen saturation. Less commonly, intubation, ventilation or even ECMO may also be required prior to the surgical intervention. As measure of patient morbidity, a composite

score of 10 variables will be used, assigning a value of 1 for each event that occurred between birth to hospital discharge or in-hospital death respectively: 1) respiratory distress syndrome requiring surfactant; 2) cardiopulmonary resuscitation requiring chest compressions; 3) cerebral vascular injury (intra-ventricular or -parenchymal hemorrhage, ischemic stroke); 4) necrotizing enterocolitis; 5) need of ECMO; 6) infections associated with health care (bloodstream, surgical site, and urinary tract infection); 7) unplanned re-intubation; 8) re-operation for residual cardiac lesions; 9) interventional catheterization for residual cardiac lesions; and 10) unplanned intensive care readmission.

6.2 Data Sources

Potential study subjects that will be identified in the Fetal Cardiac Clinic at the Hospital for Sick Children (see above). Data will be collected from the patient's health chart, echocardiography images and MRI images.

6.3 Collected Patient Data

A) Prenatal Echocardiography

- Date of exam (dd/mmm/yyyy)
- Gestational age at exam (weeks/days)
- Estimated fetal weight (g)
- MPA valve diameter
- Aortic valve diameter

Imaging variables at baseline and with MH:

Atrial septal morphology (2D; 4D) and foramen flow (color; 4D flow)

FO diameter

Septal excursion

Shunt description

Branch PA flow (mid-portion)

peak flow

VTI

PI (peak systolic velocity – end-diastolic velocity/mean velocity)

PV Doppler flow:

VTI

MPA:

VTI

Heart rate

LCO

AAo:

VTI

Heart rate

RCO

DA flow (color and Doppler):

minimal diameter

reversed end-diastolic flow: yes – no

systolic peak flow

forward-reverse flow ratio

flow restriction: yes - no
MCA Doppler flow
peak flow
VTI
PI
UA Doppler flow
Peak flow
VTI
PI

RV and LV (4D): volumes

B) Fetal MRI

- Date of exam
- Gestational age at exam (weeks+days)
- Fetal weight estimation (g)
- Fetal weight Z-score
- Fetal weight percentile
- Brain volumetry (mL) (baseline; 3D steady state)
- Placenta volumetry (mL)
- Estimated HCT
- UV
- DAo
- Ventricle (specify R or L)
- Imaging variables at baseline and with MH

Cardiovascular oximetry (SatO₂):

LV

MPA

RV

AAo

DAo

UV

SVC

Fluximetry (ml/min/m²):

AAo

DA

Main PA

RPA

LPA

SVC

IVC

UV

DA

Brain (ml/min/m²):

cDO₂
cVO₂
Fetus (ml/min/m²)

DO₂
VO₂

Placenta Volumetry
T2 star

Patient Safety during MH

- Adverse events

C) Postnatal Outcomes

- Date of birth (dd/mmm/yyyy)
- Delivery place
- Gestational age at birth
- Weight at birth
- Placental weight at birth
- APGAR score (1 and 5 minutes)
- PaO₂ and SpO₂
- Age at CCU admission
- Neonatal interventions: stat BAS, oxygen, intubation/ventilation, ECMO, other
- Neonatal PGE: yes – no; time of start
- Neonatal BAS: yes – no; age at procedure
- Pre-op/pre-BAS: hemoglobin; minimal pH; minimal preductal PaO₂; peak lactate
- Pre-BAS compromise (defined as minimal pre-BAS pH \leq 7.1, SaO₂ \leq 40%, PaO₂ \leq 25 mmHg, maximal serum lactate \geq 10 mmol): yes - no
- Pre-BAS echo: ASD and VSD size, shunting, and gradients
- Persistent pulmonary arterial hypertension (defined as combined pre-operative reverse differential cyanosis \geq 30% and/or postoperative RVp \geq 75% systemic \geq 48h post-surgery and/or \geq 50% at postoperative discharge): yes – no
- Pre-op complications: organ failure; NEC, cerebro-vascular injury; death
 - o Date of event
 - o Age at event
- Date of surgery
- Age at surgery
- Type of surgical repair: ASO; VSD closure, other
- Outcome to discharge or to 1 year if PPHT
- Morbidity score:
 - o RDS requiring surfactant
 - o CPR requiring chest compressions
 - o Cerebral vascular injury (intra-ventricular or –paranchymal hemorrhage, ischemic stroke)
 - o NEC
 - o ECMO
 - o Hospital associated infections
 - o Unplanned re-intubation

- Re-operation for residual cardiac lesions
- Interventional catheterization for residual lesions
- Unplanned CCU readmission
- Date of discharge
- Age at discharge

7. ASSESSMENT OF ADVERSE EVENTS

While no adverse events or serious adverse events (AEs or SAEs) have ever been reported in the literature and in our own experience (12) with the transient and sustained use of the study drug (MH), patient safety is an important aspect of any research study. Acute MH will be considered safe if the administration of oxygen is a) well-tolerated by the mother and fetus and b) oxygen delivery is maintained or improved during MH. This is particularly important as MH is considered a potential long-term prenatal treatment option to improve oxygen delivery to the brain.

Although an AE/SAE related to the fetus is unlikely to occur as a result of research participation, if an AE/SAE occurs, the primary physician will be responsible to identify, and to classify the seriousness, severity, causality and expectedness as follows:

a) Assessment if event qualifies as serious:

Serious Adverse Event (SAE): A SAE is any untoward medical occurrence that at any dose:

- Results in death,
- Is life-threatening,
- Requires inpatient hospitalization or prolongation of existing hospitalization,
- Results in persistent or significant disability/incapacity
- Results in congenital abnormalities or birth defect

Other events may be treated as SAEs if the physician considers it to be an important medical event that may jeopardize the participant or require intervention to prevent one of the other outcomes listed above.

b) Severity assessment:

Mild	Events are considered MILD if signs/symptoms are mild, clinical relevance is marginal, laboratory findings are asymptomatic and no specific medical intervention is required.
Moderate	Events are considered MODERATE if they require minimal, local, or non-invasive intervention only.
Severe	Events are considered SEVERE if they interrupt the participant's normal daily activities and generally require systemic drug therapy or other treatment; they are usually incapacitating.

c) Causality assessment:

Definitely related	There is a certainty that the event is related to the study drug(s).
Probably related	There is high likelihood that the event is related to the study drug(s).
Possibly related	There is a likelihood that the study drug(s) is the cause of the event, but other causes cannot be ruled out.
Unlikely related	It is not likely that the event is related to the study drug(s), and other more likely causes are present.
Unrelated	Evidence exists that the event is related to something other than a study drug.

In the event of an AE, we will use a variety of sources of information to identify possible side effects of the MH including direct observations, imaging data, participant reports, laboratory reports and other medical reports. The PI and study team will evaluate the circumstances and clinical correlation of the events. If a serious and unexpected AE occurs that is deemed to be possibly related to the use of MH (e.g. fetal death within a day of the oxygen administration), we will discontinue the use of supplementary oxygen to that study participant as applicable, immediately place the study on hold indefinitely, and the PI will report the case to the DSMB and Health Canada.

In the case of a moderate AE that is considered possibly related to the intervention (e.g. cardiac dysfunction such as fetal bradycardia of less than 90 beats per minute for more than 1 minute), we will discontinue the administration of oxygen in that study participant and the DSMB will review the event at their next scheduled meeting, and continue to enrol other patients for the study.

If an AE is mild, we will discontinue the oxygen supplementation to that study participant, but continue enrolling other patients for the study. Examples of mild maternal AEs that will result in discontinuation of oxygen administration for a subject will include fatigue, nasal or oral dryness or minor nasal bleeding and skin irritation.

In the event that oxygen supplementation is discontinued as a result of an AE, the study participant will not undergo oxygen supplementation at a later time and will be withdrawn from the study. Any data that is collected up until the point of withdrawal will be kept.

We do not expect ductal occlusion to occur within 45 minutes of fetal exposure to saturations that are lower when compared with a neonate. In the unlikely event ductal constriction occurs, it will be reversible once the MH is discontinued.

d) Expectedness assessment:

Unexpected	If the nature, severity or frequency of an event is not consistent with the risk information listed in the Material Safety Data Sheet
-------------------	---

AEs and SAEs related to oxygen administration will be documented by the site investigator. Prior to the start of oxygen administration, a thorough medical history should be obtained to document all preexisting maternal symptoms, complaints and health concerns. As many pregnancy related symptoms are intermittent in nature, a thorough history including variations in severity and frequency should be taken. AEs and SAEs should be reassessed at each participant encounter. If signs or symptoms remain similar to baseline or are less in severity, frequency, or both, they will be considered within the usual range and do not need to be documented as AEs. In contrast, signs and symptoms that are new or, if preexisting, are more frequent/severe, need to be documented, assessed for severity and causality, and followed up until resolution.

In addition, the following table of endpoints will be used for the study:

Unexpected fetal demise	Stop the study; review by DSMB, PI and collaborators
Detection of cardiac dysfunction	Discontinue the exam – observe until resolved Review by PI and collaborators
Fatigue, dry/bloody nose, skin irritation	Review by PI and collaborators

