5.2 Patient Numbers and Study Duration

Recruitment will be from the time of REB approval of this study to the time 50 patients have successfully completed the study. We follow approximately 30 women per year with a fetal

diagnosis of simple TGA, defined as TGA either with an intact ventricular septum or with ventricular septal defect(s) (VSD). The rate of pregnancy termination is low (<5%) as most affected babies do not carry a risk of significant non-cardiac disorders. Parents of a child with congenital heart disease are also highly motivated in participating in research that might help their or other children with the same condition and we anticipate that at least 80% of eligible women will be willing to participate in this research. Based on these assumptions, we anticipate being able to successfully recruit 50 participants within ≤ 2.5 years.

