6.1.2 Fetal Echocardiography

All fetal echocardiograms will be performed with standard GE Voluson E-10 or Philips IU 22 ultrasound systems within the Echo Lab facility or the Cardiac Diagnostics & Interventions Unit (CDIU) at SickKids. Fetal echocardiography poses no known risks to the mother and her fetus.

At the final visit, the mother will initially undergo a baseline fetal echocardiogram that will include the assessment of left and right ventricular outflow tract (peak flow, velocity time integral (VTI), heart rate, aortic and pulmonary valve diameters), the arterial duct (systolic and end-diastolic flow, forward/reverse flow ratio, VTI, diameter), branch pulmonary artery (peak flow, pulsatility index calculated as peak systolic velocity – end-diastolic velocity/mean velocity), pulmonary veins (VTI), atrial septum (FO diameter, atrial shunt direction and velocities, atrial septal excursion), mid cerebral artery (peak, VTI), as well as ventricular dimensions (diameter in 4CV; volumes by 3/4D). These findings will be digitally recorded and all measurements will be made offline by the responsible cardiologist to abbreviate the duration of the exam. The percent changes in flow VTIs, percent changes in flow PIs and DA forward/reverse flow ratios will be calculated using the echocardiography data.

Immediately following the baseline echocardiogram, maternal oxygen will be administered in the same room via a sterile face mask to reach about 65-70% of oxygen and delivered at a rate of 10 to 15L/minute. After a 5 minute-period to allow fetal steady-state oxygenation, the same echocardiographic variables as above will be recorded during continuous maternal O₂ supplementation, which is expected to take maximally 30 minutes or less. During the exam, the fetal wellbeing will be continuously monitored by fetal echocardiography, which allows us to continuously see the baby's movements and heart function. Oxygen supplementation will be

stopped once the above imaging variables have been obtained or after a maximum of 30 minutes (5 minutes initiation + 25 minutes echocardiogram) if the test cannot be completed within this time frame. No further research related measurements will be obtained once the MH has terminated.

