8. STATISTICS

This is an observational cohort study to test whether acute MH is a useful diagnostic test for fetal TGA. This requires confirmation of the study concept that among TGA fetuses there will be specific hemodynamic and structural characteristics and responses that will be associated with neonatal compromise shortly after birth. Neonatal compromise is defined as any of these outcomes: pre-op/BAS mortality; minimal pre-BAS pH ≤ 7.1 , SaO₂ $\leq 40\%$, PaO₂ ≤ 25 mmHg, maximal serum lactate ≥ 10 mmol; and/or PPHN (combined pre-operative reverse differential cyanosis $\geq 30\%$ and/or postoperative RVp $\geq 75\%$ systemic ≥ 48 h post-surgery or $\geq 50\%$ at postoperative discharge). Twenty-two (31%) of 70 consecutive newborns born at Mount Sinai Hospital for fetal TGA/IVS fulfilled at least one of the outcomes ([name] et al. AEPC 2016). PPHT affects 1-3% of children with TGA. Based on these data we would expect about 35 cases without severe neonatal compromise, 15 cases with neonatal compromise and 1 case with PPHT.

Simple descriptive statistics will be adequate for this small feasibility and safety study. Data obtained from this study will further help to describe the possible ranges in hemodynamic findings at baseline and during MH in a larger cohort of TGA patients and in comparison with our previous data. The comparison between pre and post MH variables will be analysed using the Brand Altman's plot. Receiver operating statistics will be used to test the diagnostic value of MH.

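### Section 7 lets acute maternal hyperoxygenation be declared safe without any bound on event risk; in 50 women, no occurrence of a given event still allows a true risk of 5.8% to 7.1%

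*Combined protocol and SAP*

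**What the plan says.** Section 7 gives a two-part criterion for the safety conclusion. The first part reads "Acute MH will be considered safe if the administration of oxygen is a) well-tolerated by the mother and fetus"; the second, joined to it, reads "b) oxygen delivery is maintained or improved during MH". The sentence that follows explains the interest: "This is particularly important as MH is considered a potential long-term prenatal treatment option to improve oxygen delivery to the brain". Section 7 does not say what counts as well tolerated, what event rate would be acceptable, or over which women the rate is taken.

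Section 8 adds no safety analysis beyond this: "Simple descriptive statistics will be adequate for this small feasibility and safety study". The Protocol Summary gives the sample size as 50. Section 5.2 ties that number to completion: "Recruitment will be from the time of REB approval of this study to the time 50 patients have successfully completed the study". Section 7 says that a woman whose oxygen is stopped because of an adverse event (AE) is withdrawn, and that her data up to then are kept.

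Exposure is capped at 30 minutes for the echocardiogram (Section 6.1.2) and 45 minutes for the MRI (Section 6.1.3). AEs during MH are on the list of collected data (Section 6.3).

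**The concern.** The Section 7 sentence is a rule for a conclusion, not background. Followed as written, an uneventful study with maintained oxygen delivery would be reported as showing that acute MH is safe, with no statement of how large a risk the data leave open. Part (b) does not fill the gap: a fetus can have maintained oxygen delivery during the test, and the cohort can still be too small to reveal an uncommon harm.

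The events that matter most here are serious and presumably uncommon. Section 7 itself uses fetal death within a day of oxygen as its example of a serious event. For such events, 50 mother-fetus pairs cannot tell a risk of zero from a risk of a few percent.

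A second difficulty lies in the denominator. Recruitment is counted in completers, while oxygen stops for AEs lead to withdrawal. If tolerability were summarised over completers, the women who did not tolerate oxygen would be left out by construction.

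**Working it through.** **Inputs.** n = 50 (Protocol Summary, Section 5.2). The tolerable rate, safety margin and confidence level for safety are not given anywhere. Unit of analysis: the woman with her fetus. Each contributes up to two exposures (Sections 6.1.2 and 6.1.3).

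**The plan's own figure.** There is none to reproduce. The sample size has no safety or precision derivation. The expected case mix in Section 8 concerns neonatal outcome and does not bear on the risk of oxygen.

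**Upper limit after no events.** The exact limit p solves (1 − p)^n = α, so p = 1 − α^(1/n).

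- One-sided 95%, n = 50: 1 − 0.05^(1/50) = 0.058, or 5.8%.
- Two-sided 95% (Clopper-Pearson), n = 50: 1 − 0.025^(1/50) = 0.071, or 7.1%.
- Cross-checks: the rule of three gives 3/50 = 6.0%; the Wilson two-sided limit is 7.1%.

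**Dependence on n.** The number starting oxygen may differ from 50:

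| Women exposed, no event | One-sided 95% | Two-sided 95% |
|---|---|---|
| 40 | 7.2% | 8.8% |
| 45 | 6.4% | 7.9% |
| 50 | 5.8% | 7.1% |
| 55 | 5.3% | 6.5% |
| 60 | 4.9% | 6.0% |

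Treating the two exposures per woman as 100 independent trials would give 3.0% and 3.6%. That is too optimistic, because both exposures fall on the same mother and fetus.

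**Chance of a clean record despite a real risk.** P(no event in 50) = (1 − p)^50. The risks below are illustrative assumptions.

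- 1%: 0.99^50 = 61%
- 2%: 0.98^50 = 36%
- 3%: 0.97^50 = 22%
- 5%: 0.95^50 = 8%

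**If one event occurs.** 1/50 = 2%, with an exact two-sided 95% interval of 0.05% to 10.6%.

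**What exclusion would need.** To exclude a given risk with no events, n must be at least ln(0.05)/ln(1 − p) (one-sided 95%). This gives 59 women for 5%, 99 for 3%, 149 for 2% and 299 for 1%. The targets are again illustrative; they show scale and are not a request for a larger sample.

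**Denominator.** Suppose, as an assumption, that three women are stopped for an AE and withdrawn before 50 others complete. Over completers the count of AE-related oxygen stops is 0/50. Over all who started oxygen it is 3/53 = 5.7%. The plan does not say which would be reported.

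**The case against.** The case for leaving the text alone has several parts.

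First, this is a small pilot. Safety is not among the objectives in Section 4 or the endpoints in Section 4.3, and the same bound applies to any event-free cohort of 50. That is true, and it is why no larger sample is asked for. But Section 8 does describe the study as one of feasibility and safety, and Section 7 supplies a verdict. A pilot can report what it excludes; it should not declare safety.

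Second, safety is already covered by AE grading, stopping provisions and a data and safety monitoring board (Sections 7 and 9.2). Those govern the conduct of the study. They do not qualify its final claim.

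Third, earlier experience is described as free of AEs. Section 7 gives no denominator for this, and Section 9.3 acknowledges that data on MH in fetal TGA are scarce.

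Fourth, descriptive statistics do not forbid confidence intervals. That is correct, but they do not require them either, and the Section 7 rule can be met without one.

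Fifth, a 6% to 7% bound is of little consequence for nasal dryness or skin irritation. This stands. The bound applies to each type of event separately and matters mainly for serious fetal or maternal events.

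Sixth, a reader might infer that the protocol means to conclude that long-term MH is safe. The text does not support that. The rule is confined to acute MH and has two conditions. Long-term treatment appears in the next sentence only as a reason for interest, and Section 2.3 keeps acute and chronic exposure apart.

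**Conclusion.** The point holds for acute MH. The plan allows an unqualified conclusion of safety, while a record of 50 women without a given event leaves a true risk of up to 5.8% (one-sided 95%) or 7.1% (two-sided 95%) for that event. Part (b) of the criterion does not narrow this.

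The figures assume 50 women who started oxygen, independent women, and complete recording of AEs. They bound the occurrence of an event from any cause: there is no comparator, so an event that does occur could not be separated from background risk by this design.

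Two stronger readings should be avoided. The protocol draws no conclusion about long-term use, so it cannot be faulted for one; it is enough to say that exposures of at most 45 minutes do not address that question. Nor does the plan say that withdrawn women will be dropped from the safety summary. Their data are kept, and what is missing is a stated denominator.

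This affects the wording and reporting of the safety result. It leaves the association between MH response and neonatal outcome untouched.

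**What to change.** In Sections 7 and 8, replace the safety declaration for part (a) with a reporting rule:

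- The safety population is every woman who started oxygen at either session, including those withdrawn after an AE.
- Report the number and percentage of women with each type and severity of maternal or fetal AE, and the number with any oxygen stop, each with an exact 95% interval. State in advance whether the limit quoted after zero events is one-sided or two-sided.
- Count women, not exposures.
- Conclude only that risks above the upper limit are excluded for acute exposure in late gestation, of at most 30 minutes for the echocardiogram and 45 minutes for the MRI.
- Add one sentence saying that the data do not address long-term MH.

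The AE data are already to be collected, and no procedure, sample size or stopping provision changes. The cost is a wording change in two sections, one extra table and a more modest safety statement.

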3. COMPLIANCE STATEMENT

This study will be conducted in full accordance with all applicable Hospital for Sick Children research policies and procedures, International Conference on Harmonisation Good Clinical Practice (ICH GCP) and all applicable regulations and the PHIPA Privacy Rule. Any episode of noncompliance will be documented.

The investigators will perform the study in accordance with this protocol, will obtain consent, and will report unanticipated problems in accordance with Hospital for Sick Children REB policies and procedures and applicable regulatory requirements. Collection, recording, and reporting of data will be accurate and will ensure the privacy, health, and welfare of research subjects during and after the study. The protocol, informed consent form(s), recruitment materials, and all participant materials will be submitted to the Research Ethics Board (REB) for review and approval.

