9.2 Data & Safety Monitoring Board (DSMB)

An independent DSMB of 4 members will monitor the progress of the study and review the safety data. The DSMB will review the result of analyses and other safety data and, if required, will provide recommendations to the study sponsor including to stop the trial if there are safety concerns.

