9.3 Regulatory and Ethical Considerations

This study involves an experimental examination for pregnant women and fetuses using supplementary oxygen for a limited period of time. Based on earlier experiences by others and our center that includes the prolonged use of MH as a potential treatment for fetuses with single ventricle physiology, no fetal and maternal AEs occurred. However, data on the use of MH for fetal TGA is scarce and therefore fetal and maternal monitoring during oxygenation warranted. All participants will be made aware of the experimental aspects of this research, and the time of oxygen administration will be kept as short as possible and will be shorter than in previous studies. In the unlikely event of a serious complication attributable to the MH we will discontinue the study.

If any incidental findings occur during the study, the study team will share the atypical findings and provide recommendations with the SickKids physician. Clinical care will be provided as needed.

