9.3.3 Reporting of Adverse Events and Serious Adverse Events

Subjects will be carefully monitored throughout their study participation. They should stop at any time they start to feel uncomfortable; even if they feel as though their ailment is unrelated to study intervention. If any unanticipated problems related to the research involving risks to subjects or others happen during the course of this study these will be reported to the REB in accordance with SickKids Policy. AEs that are not serious but that are notable and could involve risks to subjects will be summarized in narrative or other format and submitted to the REB at the time of continuing review.

All serious, unexpected adverse drug reactions to the study medication will be reported to Health Canada within 15 calendar days or for death or life-threatening events, within 7 calendar days. In the latter case, a follow-up report must be filed within 8 calendar days.

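### When non-serious fetal adverse events possibly related to oxygen repeat, no stated rule brings DSMB review forward from the next scheduled meeting

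*Combined protocol and SAP*

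**What the plan says.** Section 7 of the protocol grades the response to adverse events.

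- **Serious, unexpected and possibly related to oxygen:** the study goes on hold at once, and the DSMB and the regulator are told.
- **Moderate and possibly related** (the example is a fetal heart rate under 90 bpm lasting over a minute): oxygen stops in that participant, and "the DSMB will review the event at their next scheduled meeting, and continue to enrol other patients for the study".
- **All events:** "The PI and study team will evaluate the circumstances and clinical correlation of the events". A participant whose oxygen is stopped for an adverse event is withdrawn and not re-exposed.

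The table that closes Section 7 adds, for cardiac dysfunction, that the exam stops, followed by "observe until resolved Review by PI and collaborators". It names the DSMB only for unexpected fetal demise.

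Section 9.2 says that an independent four-member DSMB "will monitor the progress of the study and review the safety data", and that it may recommend stopping. It gives no meeting interval, event count or ad hoc provision. Section 9.3 says the study will be discontinued for a serious complication attributable to oxygen.

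There is also an ethics-board route. The investigators "will report unanticipated problems in accordance with Hospital for Sick Children REB policies and procedures" (Section 3), and Section 9.3.3 applies this where "any unanticipated problems related to the research involving risks to subjects or others happen during the course of this study". It sends notable non-serious events to the board at continuing review.

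**The concern.** The rule for moderate events works one event at a time. It treats a second or third fetal bradycardia like the first: stop oxygen in that woman, carry on enrolling, and let the DSMB see it when it next meets. The hold and stop rules require a serious event, so a run of non-serious ones need not meet them.

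Section 8 describes the study as one of feasibility and safety, and Section 9.3 concedes that "data on the use of MH for fetal TGA is scarce". Repeated, possibly related fetal cardiac events would therefore be an important new safety signal. Followed as written, the plan allows further fetuses to be exposed after such events repeat and before anyone independent of the study team has looked. How many depends on a meeting interval that the documents do not state.

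**Working it through.** **1. Accrual.** Section 5.2 gives about 30 women a year, terminations under 5%, and "at least 80% of eligible women will be willing to participate in this research". That is 30 × 0.95 × 0.80 = 22.8 a year, and 50/22.8 = 2.19 years. The plan's own figure of 50 within 2.5 years reproduces.

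**2. Women enrolled between meetings.** The interval is not given, so 3, 6 and 12 months are assumed. 22.8 × 0.25 = 5.7, 22.8 × 0.5 = 11.4 and 22.8 × 1 = 22.8, so n = 6, 11 and 23.

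**3. Three or more events in one gap.** The documents give no rate for moderate events and report none with this intervention so far, so the rate p is assumed. For one gap, X ~ Binomial(n, p). For a study of 50, P(at least one such gap) = 1 − the product of P(X ≤ 2) over the gaps (eight of 6 plus 2; four of 11 plus 6; two of 23 plus 4).

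| Rate p | One gap: 3 / 6 / 12 months | Any gap among 50: 3 / 6 / 12 months |
|---|---|---|
| 1% | <0.1 / <0.1 / 0.2% | 0.02 / 0.06 / 0.3% |
| 2% | <0.1 / 0.1 / 1.1% | 0.1 / 0.5 / 2.1% |
| 5% | 0.2 / 1.5 / 10.5% | 1.8 / 6.2 / 20.0% |
| 10% | 1.6 / 9.0 / 40.8% | 12.0 / 32.4 / 65.1% |

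**4. How often a third-event trigger fires.** P(X ≥ 3) with X ~ Binomial(50, p) is 1.4%, 7.8%, 45.9% and 88.8% at 1%, 2%, 5% and 10%.

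The plan recruits to 50 completers and withdraws anyone whose oxygen is stopped for an adverse event, so slightly more than 50 are exposed when events occur. Counting events before the 50th completer, P = 1 − Σ C(49+j, j) p^j (1−p)^50 for j = 0, 1, 2. This gives 1.5%, 8.6% and 48.5% at 1%, 2% and 5%, so the effect is small.

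**5. What the trigger gains.** The third event falls at woman k with probability C(k−1, 2) p³ (1−p)^(k−3), for k = 3 to 50. The gain is the number of women from k to the end of that gap, with meetings aligned to the start of enrolment.

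| Rate p | Mean gain when it fires: 3 / 6 / 12 months | Mean gain over all studies: 3 / 6 / 12 months |
|---|---|---|
| 1% | 2.1 / 3.8 / 7.0 | 0.03 / 0.05 / 0.10 |
| 5% | 2.3 / 4.3 / 8.5 | 1.1 / 2.0 / 3.9 |
| 10% | 2.4 / 4.7 / 9.8 | 2.2 / 4.2 / 8.7 |

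The right-hand column is the middle column times P(fires); at 5% and 6 months, 4.26 × 0.4595 = 1.96. These count women. Each has two planned oxygen sessions (echocardiography and MRI).

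**6. Whether the DSMB would already know.** For a gap that starts after s women and holds n, all three events fall in it with probability (1−p)^s × P(X ≥ 3 in n). Summing over the gaps and dividing by P(fires) gives, at 5%, 1.7%, 6.9% and 29.9% for 3, 6 and 12 months. In the remaining studies where the trigger fires, at least one earlier event has already reached a scheduled meeting.

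**The case against.** The plan is not closed to escalation. Section 7 lets the physician treat an event as serious if it is medically important, and its definition of an unexpected event includes frequency. A recurring bradycardia could by that route lead to the immediate hold. The study team evaluates every event, nothing in Section 9.2 confines the DSMB to scheduled meetings, and each exposure is capped at 30 or 45 minutes. A DSMB charter outside these documents might fix the interval and allow ad hoc review. The event rates are assumed, and at 1 to 2% the gain is very small.

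All of this stands, and it keeps the point small. None of it closes the gap. Reclassification is discretionary and has no count, and Section 7 itself offers this bradycardia as its example of a moderate event. Frequency makes an event unexpected, but the hold also needs it to be serious. Review by the study team is not independent. The documents cite no charter. The timing of the ethics-board route for unanticipated problems depends on a hospital policy that is not shown, so it can be neither credited nor faulted.

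A reader might infer that moderate events escape independent oversight, or that the closing table in Section 7 takes cardiac dysfunction away from the DSMB. The documents do not support either reading. The DSMB must review each moderate, possibly related event, and the table is introduced as an addition to the text above it.

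**Conclusion.** The point holds in a narrow form. For moderate fetal events possibly related to oxygen, the only independent review whose timing the plan ties to the event is the next scheduled DSMB meeting. No stated rule brings it forward if such events repeat, and the escalation routes that exist rest on judgement.

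The size depends on assumed rates of 1 to 10%, assumed intervals of 3 to 12 months, independent events and steady accrual. Averaged over all studies, the gain from a third-event trigger runs from 0.03 women (1%, 3 months) to 8.7 (10%, 12 months). It matters if events are fairly common and meetings are infrequent, and hardly at all otherwise. The larger means that apply when the trigger fires should not be read as the expected benefit. This is a low-cost safety improvement, and the study's validity does not turn on it.

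**What to change.** In Sections 7 and 9.2, require an ad hoc review by the existing DSMB, before the next participant receives oxygen, once a cumulative count of moderate or severe, non-serious fetal adverse events at least possibly related to oxygen is reached. Fix the count before the first exposure. The third event is a sensible default, and the DSMB may set another. State the meeting interval as well. If a charter already contains such a rule, a cross-reference is enough. Individual management and the existing hold and stop rules stay as they are.

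The cost is a short amendment and the chance of an unneeded review with a brief pause in enrolment. For a third-event trigger that chance is 1.4 to 1.5% at a true rate of 1% and 7.8 to 8.6% at 2% (50 exposed versus 50 completers). A second-event trigger would raise it to 8.9% and 26.4% with 50 exposed, which favours the third event as the default.
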